	
Primary efficacy endpoint: For all stents except UDS: Technical Success of the stents defined as Stented kidney drains (to bladder) during the planned indwell time with no re-intervention due to obstruction of the stented ureters
 
For UDS: Technical success defined as drainage following stent placement during the planned indwell time with no re-intervention due to obstruction
	unplanned re-intervention due to an obstructed ureter would mean that there is not drainage from the kidney and the study stent failed to work as indicated, and there is an adverse event or serious adverse device event related to the stent such as urinary retention, dislodging or migration of the stent
Additional		
Quality of Life (QoL) (questionnaires)	
Patient-Reported Outcomes Measurement System (PROMIS®) –
 
 • PROMIS Adult Short Form v1.0 – Pain Intensity 3a • PROMIS Adult Short Form v1.0 – Pain Interference 6b 	Gain information specific to the patient's pain scale and quality of life for subjects treated with ureteral stents
Ureteral Stent Migration	
Defined as any post procedure movement of the stent (i.e., either proximally towards the kidney or distally towards the bladder or complete distal migration) from its implant location; confirmed via imaging where necessary
 
Note: Movement of a stent by external force or inadvertent pulling is not considered a stent migrations.
	Capture real-world stent migration rates

7. Study Design

The Double-J PLUS Registry is a prospective, on-label, multi-center, global registry.

7.1. *Scale and Duration*

The registry will include:

- Up to 1,000 subjects will be enrolled at up to 35 sites
- At least 142 subjects will be enrolled for Tria™ Ureteral stent for stone management at sites within the United States, Europe, Canada and Japan. A hypothesis test will be performed for this patient group.
- Target enrollment for each additional stent type as outlined below.
- The enrollment period will be approximately 30 months.
- There will be up to 15 sites in the United States; 10 in EU, 5 in Canada and 5 in Japan.
- The study is expected to take 50 months from first subject enrollment until the study closeout.
- Each subject will be involved in the study for approximately 8 weeks to 15 months depending on the stent indwell time, from the index procedure.

Boston Scientific Ureteral Stents	Target Enrollment	Minimum Target Enrollment
• Tria Soft and Tria Firm	142	142

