11.1.1. Primary Efficacy Endpoint – Technical Success

The primary efficacy endpoint is the technical success of Tria™ in stone management. For all stents except UDS, technical success is defined as stented kidney drains (to bladder) during the planned indwell time with no re-intervention due to obstruction of the stented ureter(s). For UDS, technical success is defined as drainage following stent placement during the planned indwell time with no re-intervention for obstruction. Restenting with a new study stent may only occur during the initial stent placement procedure for such situations as stent misplacement, improper stent size choice, or other conditions, as necessary and will not be considered as a primary effectiveness endpoint failure or a secondary endpoint failure for stricture resolution.

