11.1.1.1. Hypotheses

The study will evaluate whether Tria™ stents have technical success during planned indwell in more than 85% in stone management. The null and alternative hypotheses for this evaluation are

$H_0: p \leq 85\%$ $H_1: p > 85\%$

where p is the proportion of stented ureter(s) with technical success.

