11.1.1.2. Sample Size

There are two published studies on the patency in the stone management for Double J stents. The success rates were 98% with a 95% CI [94%, 99%] (Calvert, et al., 2013) and 96% with a 95% CI [92%, 99%] (El-Faqih SR, 1991). As a result, an 94% patency rate is estimated as the performance for the Double J stents. The performance goal of 85% is chosen for the patency for TRIA in the stone management, with a non-inferiority margin of 9%.

With a one-sided type I error of 0.025 and a type II error of 0.10 (90% power), a sample size of 127 subjects with Tria™ placed at least 12 hours for stone management are needed to demonstrate the proportion of stented ureters with technical success exceeds 85%. Assuming a 10% attrition rate, at least 142 stone management subjects with Tria™ stent procedures where stents indwell at least 12 hours are required.

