11.1.1.3. Statistical Methods

The hypotheses above will be evaluated based on the two-sided 95% exact Clopper-Pearson confidence interval for the proportion of stented ureters with technical success. Only stents placed at least 12 hours will be included in the analysis. If the lower bound of the confidence interval exceeds 85%, the alternative hypothesis will be demonstrated. Sensitivity analysis to missing data will be performed using tipping-point analysis.

In addition, a Generalized Estimating Equation (GEE) model will be used to estimate the technical success rate to account for within-subject correlation due to bilateral stent placement if applicable.

Descriptive statistics including 95% confidence intervals will be utilized to summarize the technical success rates for the non-stone management subjects treated with Tria™ stents respectively.

For non Tria™ ureteral stents in the study, the technical success rates will be summarized by descriptive statistics including 95% confidence intervals by indication (i.e. stone management, benign obstruction, malignant obstruction, ureteral dysfunction, bladder cancer, and other as applicable) respectively for each device type. Only stents placed at least 12 hours will be included in the analysis.

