11.2. General Statistical Methods

11.2.1. Analysis Sets

The Intent-to-Treat (ITT) subject population includes all subjects who provide written informed consent to be enrolled into the study, and have the stent placement procedure initiated.

The As Treated (AT) Population includes all subjects for whom the stent placement is completed.

The Per Protocol (PP) population includes all subjects in the AT Population who meet all eligibility criteria.

The endpoint analyses will be performed for the ITT population. The AT and PP populations will be evaluated as sensitivity analyses for the primary efficacy endpoint and the safety outcomes will also be assessed using the AT population.

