11.2.2. Control of Systematic Error/Bias

All subjects will be treated according to the directions in the Operating Manual and IFU/DFU.

The primary efficacy endpoint analysis based on the exact Clopper-Pearson confidence interval is specified to be conservative in order to avoid bias towards demonstrating the primary hypothesis (i.e., achieving the performance goal) of the study. Furthermore, the potential of bias from missing data for the primary efficacy endpoint will be assessed through tipping point analysis.

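### The 12-hour inclusion rule removes from the only pass/fail test stents explanted or replaced early for obstruction, which the endpoint definition counts as technical failures

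*Combined protocol and SAP*

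**What the plan says.** Section 11.1.1 defines technical success for all stents except urinary diversion stents as "stented kidney drains (to bladder) during the planned indwell time with no re-intervention due to obstruction". It sets no minimum time in place. The one exemption is restenting at the index session: "Restenting with a new study stent may only occur during the initial stent placement procedure", and this is not scored as a failure. Section 6 gives the reasoning behind the endpoint: "unplanned re-intervention due to an obstructed ureter would mean that there is not drainage from the kidney and the study stent failed to work".

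The hypotheses in 11.1.1.1 are H0: p ≤ 85% against H1: p > 85%, "where p is the proportion of stented ureter(s) with technical success". Section 11.2.1 adds: "The endpoint analyses will be performed for the ITT population". Neither carries a time condition.

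Section 11.1.1.3 then tests the hypotheses with the two-sided 95% Clopper-Pearson interval and restricts the data: "Only stents placed at least 12 hours will be included in the analysis". The synopsis repeats this. Section 11.1.1.2 uses the same restriction ("a sample size of 127 subjects with Tria™ placed at least 12 hours for stone management are needed") and its attrition sentence shows that it refers to indwell time. No exception is made for a stent that came out early because it failed.

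**The concern.** A stent replaced for obstruction at, say, hour 8 is a failure under 11.1.1 but appears in neither the numerator nor the denominator of the test. This is the only powered hypothesis in the registry, and the safety endpoint has no pass/fail criterion (11.1.2.1).

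The filter acts on something that happens after placement. Section 4.1 gives 48 hours as the shortest indwell and the synopsis places removal typically from 2 weeks, so exits before 12 hours are essentially unplanned, and failure of the stent is one reason for them.

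Nothing planned clearly puts these stents back. The tipping-point analysis addresses missing data. The As Treated and Per Protocol sets are defined by subject and say nothing about restoring excluded stents. Participation ends when the study stent is replaced (9.4), so the ureter does not return through its new stent. Early events still reach the adverse event, SADE and device deficiency records, but these do not feed the test.

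At stake is what a pass means: success above 85% among all stented ureters, or only among stents that lasted 12 hours.

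**Working it through.** **Inputs from the plan.** Performance goal 85%, assumed true rate 94%, one-sided type I error 0.025, power 90%, 127 evaluable and 142 after 10% attrition (11.1.1.2); Clopper-Pearson lower bound above 85% (11.1.1.3). **Assumed:** one ureter per subject; a share e of placed stents that are obstructive failures before 12 hours. The documents give no value for e.

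**Plan's own figures.** The lower bound for x successes in n is the 2.5% quantile of Beta(x, n − x + 1). At n = 127 the smallest passing count is 116. The chance of 116 or more is 0.0245 at p = 0.85 and 0.920 at p = 0.94. No smaller n reaches 90% power, and 127/0.9 rounds up to 142. The stated sample size is reproduced.

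**Boundary cases.** Restoring one dropped failure adds 1 to the denominator only.

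| Retained data | Lower bound | One failure restored | Lower bound |
|---|---|---|---|
| 116/127 | 85.03% (passes) | 116/128 | 84.20% (misses) |
| 130/142 | 85.70% (passes) | 130/143 | 84.96% (misses) |

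**Chance of passing when all-stent success is exactly 85%.** If early obstructive failures are dropped, success among retained stents is 0.85/(1 − e); for e = 1% this is 0.85/0.99 = 0.8586. The chance of passing is the binomial probability of at least 116 of 127, or at least 130 of 142, at that rate. The share of all failures that fall before 12 hours is e/0.15.

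| e | Share of failures | 127 retained | 142 retained |
|---|---|---|---|
| 0 | 0% | 2.45% | 1.5% |
| 1% | 7% | 4.4% | 2.8% |
| 2% | 13% | 7.5% | 5.2% |
| 3% | 20% | 12.5% | 9.4% |

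**If failures do not cluster early.** With a constant hazard over an illustrative 14 days, e = 1 − exp(ln(0.85) × 0.5/14) = 0.58%, and the chance of passing is 3.4% (127) or 2.1% (142). Over 28 days it is 2.9% or 1.8%; over 90 days, 2.6% or 1.5%. At 142 it stays below 2.5% until e is about 0.8%.

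**Other early exits.** If the rule instead drops 1% early successes, retained success is 0.84/0.99 and the chance of passing falls to 2.2% (127) or 1.3% (142). If it drops 1% of each kind, retained success is 0.84/0.98 and the chance is 4.0% or 2.5%.

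**With early obstructive failures counted.** Enrolment continues to n retained stents, the number k of early failures is negative binomial, and the threshold is taken at n + k. No other early exits are assumed. At all-stent success of 85% and e = 1%, 2%, 3%, the chance of passing is 2.3%, 2.2%, 2.1% (127) and 1.6%, 1.9%, 2.0% (142). At 94% with 127 retained, power is 92.0%, 91.3% and 90.6% for e = 0, 1% and 2%.

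**The case against.** The rule is prespecified, appears consistently in the synopsis, the sample size and the test, and filters on time, not on outcome. For stents in place at least 12 hours the test is valid, with exact size 2.45% (127) or 1.5% (142). A stent that obstructs early but stays in for 12 hours is still counted as a failure. This all stands, but it describes a narrower population than 11.1.1 and 11.1.1.1 do.

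The size is hypothetical. The 2% and 3% cases need 13% and 20% of all failures to fall in the first 12 hours, and the boundary example needs an exact count: 116 of 127 has a probability of about 6% at a true 94%. This also stands; only the direction is certain.

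Some supporting text is open to interpretation. The 12-hour sentence sits in the Clopper-Pearson paragraph and again in the non-Tria paragraph, so whether it governs the GEE estimate and the As Treated and Per Protocol analyses is unclear. Section 11.2.2 says the Clopper-Pearson analysis "is specified to be conservative in order to avoid bias towards demonstrating the primary hypothesis", which may refer only to the interval method. Neither reading changes the pass/fail test.

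The most substantive objection is to the remedy. Adding early stents only when they failed makes inclusion depend on outcome and on an open-label removal reason, whereas a set of all placed stents would not. That is a fair criticism; adjudication and an all-placed sensitivity analysis are the answer to it.

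**Conclusion.** The concern holds. Followed exactly, the plan leaves failures by its own definition out of its only pass/fail test, and for early obstructive exits the omission can only raise the lower bound.

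With 127 retained stents, the chance of passing at a true 85% rises from 2.45% to between 4.4% and 12.5% if 1% to 3% of stents are such failures; with 142 it rises from 1.5% to between 2.8% and 9.4%. These rates are assumed. Under the constant-hazard illustrations the effect is small, and exits for other reasons, such as dislodgement, can move the estimate either way because 11.1.1 does not say how they are scored. The contradiction between sections is certain and its practical size is unknown. It should be fixed because correction is cheap and a borderline result could turn on one stent.

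**What to change.** 1. In the synopsis and 11.1.1.3, count as a technical failure in the primary analysis any stent explanted, replaced or re-intervened on for obstruction or non-drainage at any time after the initial placement procedure, including before 12 hours. Keep the 11.1.1 exemption for restenting during that procedure.
2. Have the Independent Medical Reviewer, who already adjudicates relevant Tria events (20.2), classify every Tria stone-management exit before 12 hours. Report counts and reasons.
3. Prespecify two sensitivity analyses: (a) all placed stents in the denominator, with early exits without obstruction handled in the tipping-point analysis; (b) the present set of stents in place at least 12 hours. State which set the GEE, As Treated and Per Protocol analyses use.
4. Reconcile 11.1.1.1, 11.1.1.2 and 11.2.1 with the chosen set. The intent-to-treat set also includes subjects whose procedure began but who received no stent, so it cannot be applied literally to stented ureters.

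**Cost.** Changes of wording and one line in the reviewer's charter. Placement and explant times are already recorded (10.6, 10.8), and visits for suspected obstruction already seek stent performance, adverse event, device deficiency and imaging data (10.10). Removal reason is not a listed item in 10.8, so it needs one eCRF field or must be taken from those records. The reported success rate may be slightly lower. The sample size stays as it is, provided 94% is the success rate with early failures counted.

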11.1.2. Primary Safety Endpoint - SADE

The primary safety endpoint is serious adverse device effect related to the study stent(s) implanted.

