Indication(s) for Use	
Boston Scientific Ureteral Stents are indicated for use to facilitate drainage from the kidney to the bladder, via endoscopic or fluoroscopic placement by a trained physician
 
Boston Scientific Urinary Diversion Stents are indicated for drainage following percutaneous, endoscopic, or operative procedures

Device/System applied as Standard of Care	
Boston Scientific Ureteral Stents, including (but not limited to):
 
• Contour™ Ureteral Stent• Contour VL™ Ureteral Stent• Contour™ Injection Ureteral Stent• Contour VL™ Injection Ureteral Stent• Percuflex™ Ureteral Stent• Percuflex™ Plus Ureteral Stent• Percuflex™ Urinary Diversion Stent (UDS)• Polaris™ Ultra Ureteral Stent• Polaris™ Loop Ureteral Stent• Tria™ Soft Ureteral Stent• Tria™ Firm Ureteral Stent• Contour™ SureDrive™ Steerable Ureteral Stent Set• Contour VL™ SureDrive™ Steerable Ureteral Stent Set• Percuflex™ Plus SureDrive™ Steerable Ureteral Stent Set
Study Design	A prospective multi-center global registry

Boston Scientific Double-J PLUS Ureteral Stent Postmarket Patient Registry DJUS PLUS Registry	
	<pre> graph TD A([Informed Consent and Eligibility Informed consent form and HIPAA Authorization signed by patient Eligibility check]) --> B{Subject meets enrollment criteria Signed ICF and met eligibility criteria} B -- No --> C([Screen Failure No further study activities]) B -- Yes --> D[Baseline Assessments Demographics, Medical History, Lab tests - Blood test and Urinalysis, QOL questionnaires] D --> E{Index Procedure Ureteral Stent Implant, Stent Performance, Medications, AE Assessment} E -- No --> F([Stent Placement not successful No further study activities]) E -- Yes --> G{Planned indwell greater than 90 days} G -- Yes (Long-term ≥90 days indwell) --> H[Post-Procedure Follow-up (≤ 90 days from Index procedure) Stent Performance and AE Assessment] G -- No (Short-term ≤ 90 days indwell) --> I[Stent Removal Visit (up to maximum indwell time as indicated in individual stent DFU/IFU) Stent Performance, Stent explant, QoL questionnaire and AE assessment] I --> J[Post-Stent Removal Visit (3-12 weeks from Stent Removal Visit) AE Assessment, QoL questionnaire Lab tests - Serum Creatinine and GFR (if SOC)] J --> K{Is a new stent placed?} K -- Yes --> L([End of Study]) K -- No --> J </pre>
Planned Number of Subjects	Up to 1,000 subjects in the Registry. Target enrollment of 25 subjects per stent type, unless otherwise noted

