9.2.2. Involuntary Withdrawal

Subjects may be involuntarily withdrawn from the study if the Investigator determines it is in the subject's best interest. If the subject is withdrawn at the investigator's discretion, the reason for withdrawal must be documented in the subject's medical records. Subjects who did not receive the study stent (implant failures) will be followed through hospital discharge and will be considered withdrawn.

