11.1.2.1. Hypotheses

There is not a pre-specified pass/fail hypothesis for this endpoint.

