11.1.2.2. Statistical Methods

Rates of serious adverse device effects will be summarized using descriptive statistics (event counts, proportion of subjects with a SADE) for each study stent type implanted respectively.

In addition, all AEs will be summarized by relatedness to procedure and/or device for each study stent type implanted respectively.

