18.2. Definitions and Classification

Safety definitions are provided in Table 18.2. Administrative edits were made on the safety definitions from applicable regulations and guidance including (but not limited to) 21 CFR Part 812, ISO 14155 and EU MDR 2017/745/MDCG 2020-10/1 Guidance on Safety Reporting in Clinical Investigations for clarification purposes.

Table 18.2: Safety Definitions

Term	Definition
Adverse Event (AE) Ref: ISO 14155 Ref: MDCG 2020-10/1	Any untoward medical occurrence, unintended disease or injury, or any untoward clinical signs (including an abnormal laboratory finding) in subjects, users or other persons, in the context of a clinical investigation, whether related to the study medical device and whether anticipated or unanticipated. NOTE 1: This includes events related to the study medical device or comparator. NOTE 2: This definition includes events related to the procedures involved. NOTE 3: For users or other persons, this definition is restricted to events related to the study medical device.
Adverse Device Effect (ADE) Ref: ISO 14155 Ref: MDCG 2020-10/1	Adverse event related to the use of the study medical device. NOTE 1: This includes any adverse event resulting from insufficiencies or inadequacies in the instructions for use, the deployment, the implantation, the installation, the operation, or any malfunction of the study medical device. NOTE 2: This definition includes any event resulting from use error or from intentional misuse of the study medical device. NOTE 3: This includes ‘comparator’ if the comparator is a medical device.
Serious Adverse Event (SAE) Ref: ISO 14155 Ref: MDCG 2020-10/1	Adverse event that led to any of the following: a) death, b) serious deterioration in the health of the subject, users or other persons as defined by either: 1) a life-threatening illness or injury, or 2) a permanent impairment of a body structure or a body function, including chronic diseases, or

Table 18.2: Safety Definitions

Term	Definition

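### The SADE endpoint in Section 11 is tied to stents implanted, which conflicts with the synopsis, Section 6, the device-effect definition and the ITT rule, and leaves failed placements without a row or denominator

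*Combined protocol and SAP*

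**What the plan says.** The statistical section sets the primary safety endpoint in 11.1.2: "The primary safety endpoint is serious adverse device effect related to the study stent(s) implanted". Section 11.1.2.2 summarises it as "event counts, proportion of subjects with a SADE) for each study stent type implanted respectively", and summarises all adverse events by the same grouping. Section 11.1.2.1 adds: "There is not a pre-specified pass/fail hypothesis for this endpoint".

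Other parts of the document are wider:

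- The synopsis and the table in Section 6 name the endpoint as SADEs, with no reference to whether a stent was implanted.
- Table 18.2 (Section 18.2), note 1 to the adverse device effect definition: "This includes any adverse event resulting from insufficiencies or inadequacies in the instructions for use, the deployment, the implantation". A SADE is a device effect with a serious outcome, so it inherits this scope.
- Section 11.2.1 defines ITT as "all subjects who provide written informed consent to be enrolled into the study, and have the stent placement procedure initiated". It assigns the endpoint analyses to ITT and adds an As Treated (AT) assessment of safety, where AT requires a completed placement.
- Section 11.1.1 permits a new study stent to be placed during the initial procedure when the first is unsuitable.

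On subjects in whom placement fails, Section 9.2.2 says: "Subjects who did not receive the study stent (implant failures) will be followed through hospital discharge and will be considered withdrawn". Section 9.4 agrees. The flow chart in the synopsis instead labels that branch "Stent Placement not successful No further study activities".

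**The concern.** A subject whose placement was started but not completed belongs to ITT and may have suffered a serious device effect as the protocol defines it. That subject has no implanted stent and no implanted stent type. Sections 11.1.2 and 11.1.2.2 therefore offer no row for the event and no denominator for the subject, and no other rule assigns them. A SADE caused by a study stent that was tried, discarded and replaced in the same session is also hard to place, because the stent that caused it is arguably not the stent implanted.

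The endpoint has no hypothesis, so the descriptive per-type rates are the whole primary safety result. If the analyst follows Section 11 to the letter, the analysis labelled ITT is effectively conditioned on successful delivery of the device, and the contrast with AT that Section 11.2.1 sets up largely disappears.

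**Working it through.** **1. No stated figure to reproduce.** The safety endpoint has no assumed rate, margin or sample size. The check is a comparison of the texts, followed by an illustration with assumed counts.

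**2. Two kinds of subject traced through the rules.**

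| Subject | In ITT (11.2.1) | In AT (11.2.1) | Row under 11.1.2.2 | SADE within 11.1.2 as worded |
|---|---|---|---|---|
| Placement started, no study stent left in place | Yes | No | None | No: no stent was implanted |
| First study stent discarded, second implanted, harm from the first | Yes | Yes | That of the implanted stent | Arguably not: the causal stent was not implanted |

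ITT and AT differ mainly by the first kind of subject. Tabulating "for each study stent type implanted respectively" leaves out that same kind of subject, so the ITT table comes close to the AT table. The ITT entry in Table 26.2 adds eligibility but still asks only that the index procedure be initiated, so it does not change this.

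**3. Direction and size.** Let *m* subjects have completed placements with *s* SADE subjects among them, and *k* have failed placements with *e* SADE subjects among them.

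- Rate by type implanted: *s/m*
- Rate by ITT: *(s + e)/(m + k)*
- Difference, ITT minus implanted: *[k/(m + k)] × (e/k − s/m)*

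The implanted-only rate is too low only when *e/k* exceeds *s/m*, that is, when SADEs are more frequent in failed than in completed placements.

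Group sizes of 15 (minimum), 25 (target) and 142 (Tria) come from Section 7.1 and are treated here as ITT counts. **All failure and SADE counts are assumptions.** Exact 95% Clopper-Pearson limits are shown where calculated; the plan itself specifies no interval for SADEs.

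| ITT size | *k* | *s* | *e* | By type implanted | By ITT |
|---|---|---|---|---|---|
| 15 | 1 | 0 | 1 | 0/14 = 0% (0.0 to 23.2) | 1/15 = 6.7% (0.2 to 31.9) |
| 25 | 1 | 0 | 1 | 0/24 = 0% (0.0 to 14.2) | 1/25 = 4.0% (0.1 to 20.4) |
| 142 | 3 | 0 | 1 | 0/139 = 0% (0.0 to 2.6) | 1/142 = 0.7% (0.0 to 3.9) |
| 142 | 3 | 2 | 1 | 2/139 = 1.4% | 3/142 = 2.1% |
| 142 | 3 | 2 | 0 | 2/139 = 1.44% | 2/142 = 1.41% |

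The last row shows the opposite direction: with no SADE among the failures, the implanted-only rate is marginally too high.

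**4. Collection.** The flow chart puts adverse event assessment inside the index procedure step, before the branch for unsuccessful placement, and Section 18.1 makes SADEs reportable from the index procedure. An event during the attempt is therefore collected under either text. The chart and Sections 9.2.2 and 9.4 differ only over the interval from the end of the procedure to discharge.

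**The case against.** The strongest reply is that nothing is actually lost. The synopsis and Section 6 carry no implant restriction, Section 18.1 requires these events to be reported, and Section 11.2.1 names ITT for endpoints with AT as an addition, which suggests that failed placements were meant to count. The phrase in 11.1.2 can also be read as naming the device of attribution, since Section 10.6 assesses accessories separately, and not as limiting which subjects are counted. There are no table shells to show what will be produced.

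Much of this stands, and it rules out three stronger readings that a reader might infer:

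- *That harm in failed placements certainly drops out of the safety result.* It is reportable, and it falls within the endpoint as defined in the synopsis and Section 6. Omission is the literal effect of Section 11, not a settled outcome.
- *That the per-type rate is biased downward.* The direction depends on an unknown comparison of SADE frequency in failed and completed placements.
- *That a SADE from a discarded stent is both excluded and credited to another type.* These are alternatives. If 11.1.2 excludes the event, it cannot also be counted under the replacement's type.

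Loss of events after discharge does follow from treating these subjects as withdrawn. However, Section 9.2 has the investigator ask permission to follow the subject outside the study when withdrawal is due to device safety or performance.

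The reply does not remove the contradiction. Section 11 is the statistical text and is narrower than the rest. Even under the wider endpoint, 11.1.2.2 supplies no row or denominator for a subject without an implanted stent.

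**Conclusion.** The point holds as an internal contradiction with a practical consequence: Sections 11.1.2 and 11.1.2.2 disagree with the synopsis, Section 6, Table 18.2 and the ITT rule on whether failed placements and discarded stents count in the primary safety result.

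Its size cannot be determined, because the documents give neither a placement-failure rate nor a SADE rate. Under the assumed counts, one SADE in a failed placement moves the rate by 6.7 points in a group of 15, 4.0 points in a group of 25 and 0.7 points among 142. It therefore matters most for the small stent-type groups. No hypothesis test or decision rule is affected.

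**What to change.** - **Section 11.1.2:** define the endpoint as *SADE related to any study stent implanted or attempted*, in line with the synopsis and Section 6.
- **Section 11.1.2.2, ITT analysis:** attribute each SADE to the stent judged causal, include subjects with a failed placement in the denominator of the type attempted, and show them on a separate line, *attempted, not implanted*. Keep type implanted as the grouping for the AT analysis.
- **Flow chart and Sections 9.2.2 and 9.4:** reconcile what is collected, and until when, for subjects in whom placement fails.

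Tabulating everything by the first type attempted would not be a good substitute. It would file events from the indwell of a second, implanted stent under a type that was not left in place. An extra follow-up contact is not needed to reconcile the text.

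The cost is wording in three places and one extra table line. The downside for the sponsor is that the reported SADE rate may be slightly higher.
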